#### SCCS

A pre-vaccine baseline risk period will be applied to control for the healthy-vaccinee effect. The SCCS will include age in days, and season (classified from the month) as time-varying covariates, as well as all available doses of pertussis vaccine as exposures. Conditional Poisson regression analyses will be conducted for the estimations.

10 describes the availability of wP information of two different databases (i.e. in database [Db] A, wP information is available and in Db B it is not) and the approach how IR within the risk period will be calculated.

**Figure 4: Approach How to Calculate Risk Window Specific IR in Databases where wP Information is Either Available or Lacking**

### 7.2.9. Limitations

In this POC feasibility study that tests and evaluates the ADVANCE system, tailored to generate rapid evidence on vaccine effects, there are several methodological limitations. These limitations will be assessed, and are an integral part of the system evaluation process. The following points are considered to be the expected limitations:

- Given that this POC feasibility study evaluates a system and its different processes, the epidemiological results produced (i.e. incidence rates and risk ratios) should not be considered as evidence that can be directly translated to inform epidemiological and pharmacovigilance decision-making processes. The epidemiological results produced in this POC feasibility study are part of a set of evaluation indicators to test the ADVANCE system and may not be the best or true estimates
- It could be possible that within the process of database selection it will become evident that proposed case definition(s) for the events are either different, or are differently interpreted, in a specific database or country. Different countries and databases could be using different case definitions. To address this limitation, the study will produce country-and database-specific analyses and results.
- Some event outcomes are signs and symptoms and not disease entities. The coding in databases might not be applicable to signs and symptoms (e.g. crying). Therefore, database extraction algorithms and strategies need to be adapted (e.g. include also free text search).
- Event codes in databases might contain the whole spectrum of potential, probable and confirmed cases. Given the POC feasibility study nature to test the system and to save costs and time, diagnostic codes will not be validated on a patient level using medical histories and charts.

- 
- It is expected that only a limited number of databases will have information on wP vaccination available. Therefore, the suggested strategies in the methods sections 7.4.3 (i.e. multiplying baseline incidence rates with IR ratios across databases, time periods, and wP/ aP data) will be applied. The additional use of literature information will be carefully evaluated and interpreted.
  - The type of database used (e.g. GP database, hospital database, claim database, etc) will influence incidence rates. To address this limitation, the study will produce country/ database-specific analyses and results.
  - The current methodology will not account for differences in vaccination schedules: different countries use different vaccines and schedules that may have changed over time. ATC codes will be used to identify which types of vaccines were used; this will allow stratification on vaccine types. Further, risks on schedule level will not be evaluated but will be evaluated on a dose level as each case is followed after each dose given.
  - Misclassification or missing information on vaccinations and events is a common limitation of observational studies conducted in electronic healthcare databases. Missingness and misclassification will be carefully followed and attempts will be made to implement data cleaning procedures (e.g. probability of wP or aP vaccine given the time of administration, dose according to timing in vaccination schedule, etc). Records with missing dates (i.e. birthdates, data of vaccination, date of event occurring) will be excluded. ATC code is a mandatory data field. A missing dose information will be derived (i.e., dose will be per recommendation, as determined by the database custodian based on knowledge of the local immunization schedule and as documented in an analytic variable generated for the purpose of the study).
  - aP and wP vaccine administration could have been overlapping. The period of potential overlap in a database will be excluded if aP or wP vaccine type information is missing (i.e. database entry is only referring to 'pertussis vaccine' and aP or wP is not specified).
  - The smallest possible time unit in electronic healthcare databases is 'days'. This could potentially make it difficult to judge whether vaccination happened before the event or vice versa when recorded on the same day. In this study, it is assumed a priori that vaccination occurs before the event whenever they are recorded on the same day, so the vaccination day is classified as risk period and starting at Day 0.

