**Figure 2: Recommended Pertussis Schedules from ECDC Report on Pertussis Vaccine Shortage (October 2015)**

The World Health Organization (WHO) standards of childhood pertussis vaccination recommend a three-dose primary series administered between 6 weeks and 6 months of age, followed by a booster dose, preferably in the second year of life. As previously mentioned, various countries have adapted and customized their vaccination schedules according to their policy considerations. As of March 2015, 19 countries use a three-dose schedule for the primary series, either at 2-3-4 months of age (n=9) or 2-4-6 months of age (n=10). Most of these countries give a toddler booster dose towards the end of the first year of life (n=3) or during the second year of life (n=13). In one country this booster dose can be administered before or after the first birthday; two countries do not recommend any toddler booster dose. Seven countries administer a two-dose primary series at three and five months of age, followed by a booster for 12 month-olds. Only France has a two-dose schedule at two and four months of age followed by a booster at 11 months of age.

All countries, except Malta, recommend one (n=11), two (n=15) or three (n=4) further aP booster doses between two and 18 years of age.

Six countries recommend one or more aP booster doses for all adults and/or elderly. Two countries (United Kingdom and Ireland) only target pregnant women in their last trimester of pregnancy (since late 2012).

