#### **7.2.5. Population Selection**

The study population will comprise all children registered in any of the participating databases during the study period and for whom an adequate start and end of follow-up and date of birth can be defined. Children will be followed from start of the study period, one month after date of birth (i.e. to allow for pre-vaccination time for the SCCS design and to avoid pre-term related or birth-induced increase in incidence rates), or date of valid data in the database (whichever is the latest) until the end of study period (31-12-2015, the school-entry pertussis booster, transferring out of the database, death, reaching age 6 years: whichever is the earliest). Persons with missing dates of birth or sex will not be included.

For the incidence rate part of the study, we will retain all subjects meeting age and calendar time inclusion criteria with person time greater than zero.

The vaccination day and outcome-specific risk-windows after vaccination will be classified as risk periods, and the period between the end of the risk-window after vaccination until the next pertussis-containing vaccination or end of follow-up as the baseline period. To keep track of dose these periods will also be labeled by the number of previous pertussis-containing vaccinations. For all eligible subjects, CohortStart will be equal to PopulationStart and CohortEnd equal to PopulationEnd.

Databases will be asked to provide dates during which both wP and aP pertussis vaccines were both being used in the population. Patient time during the period of the switch from wP to aP will be removed from the cohort and SCCS analyses to avoid misclassification of exposures.

In order to avoid confounding by infections or other vaccinations, the study population for the incidence rate cohort design will NOT be the same as for the SCCS design.

For the self-controlled case series, analysis sets containing cases of each of the outcomes under study will be defined. For each of these cases, exposure will be defined as: exposed to wP and exposed to aP.

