#### EXPOSURE WINDOWS

Person time of follow up in the cohort will be categorized as risk and baseline periods. Persons will be followed up over the whole period independent of occurrence of an event or vaccination. Person time will not be stopped at the occurrence of an event or vaccination. The vaccination day and outcome-specific risk-windows after vaccination will be classified as risk periods, and the period between the end of the risk-window after vaccination until the next pertussis-containing vaccination or end of follow-up as the baseline period. To keep track of dose, these periods will also be labelled by the number of previous pertussis-containing vaccinations.

---

Outcome	Risk Window After Vaccination
Injection site reactions	0-7 days
Fever	0-72 hours
Somnolence	0-48 hours
Persistent crying, irritability	0-24 hours
Generalized convulsions	0-72 hours
HHE	0-48 hours
Extensive limb swelling	0-7 days

---

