### 7.2.8.3. Statistical Methods

#### COHORT STUDY

The incidence rate of each event will be calculated using a dynamic cohort approach. For each person in the cohort, follow-up time will be classified by calendar year, sex, age in year of birth and months and the different risk window (see exposure section). This persontime will be the denominator for the incidence rate calculations. Incidence rates will be calculated stratified by:

1. type of vaccine: wP/aP
2. database, country
2. dose of wP/aP (actually received dose)
3. risk window
4. age in months and year of birth
5. calendar year

[figure not shown]
Cases will be counted in the numerator for the rate calculation if the date of onset/occurrence of an event falls into the specific window of that vaccine, and will be further stratified to count in the correct age/sex and calendar year category at the date of onset.

A Poisson distribution will be used to calculate 95% CIs.

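### Filling a missing dose number from the recommended schedule contradicts stratifying by the dose actually received, and a simple count also fails where vaccination history is incomplete

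*Protocol*

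**What the plan says.** Dose enters the analysis in three places.

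- Section 7.2.5 (Population Selection) has risk and baseline periods "labeled by the number of previous pertussis-containing vaccinations". The Exposure Windows text in 7.2.7.1 repeats this.
- Section 7.2.8.3 (Cohort Study) stratifies incidence rates by "dose of wP/aP (actually received dose", alongside database, country, risk window, age in months and calendar year.
- Section 7.2.9 (Limitations) says "A missing dose information will be derived", and then that "dose will be per recommendation, as determined by the database custodian based on knowledge of the local immunization schedule", documented in an analytic variable.

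The same section adds "Records with missing dates (i.e. birthdates, data of vaccination, date of event occurring) will be excluded". It also says that differences in vaccination schedule are not accounted for and that "risks on schedule level will not be evaluated but will be evaluated on a dose level".

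Table 5 (section 7.2.3) plans to cross-tabulate recorded, derived and sequence dose and to count vaccination records without a dose. Nothing in the protocol says which source defines dose when they disagree. Table 6 (section 7.3.1) asks for risk-window incidence by dose and for baseline incidence by age in months.

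**The concern.** A recommended dose and a received dose are the same only for children vaccinated on time with none missed. For the others, the 7.2.9 rule places the event and its risk window in a dose stratum that the child had not reached, which contradicts the stratifier in 7.2.8.3.

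A running count does not fully repair this. Follow-up can begin at the date of valid data, after some doses have been given. If those doses are not held, the next one is counted as dose 1. If an undated dose record is dropped, every later count falls by one, and the risk days of the dropped dose pass into baseline or into time before any dose.

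The risk-window rows of Table 6 are per dose and feed the benefit-risk model. Section 5 reports that reaction frequencies changed over successive doses, so the dose label carries information. The two errors also pull in different directions: the schedule rule can put a true first dose into the dose-3 stratum, while an incomplete count can put a true third dose into the dose-1 stratum.

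**Working it through.** The plan states no figure for dose misclassification, so there is none to reproduce. The check has four steps.

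**1. The two rules on one child.** Schedule 2-3-4 months (section 5). A child receives a first pertussis dose at 4 months and the record has no dose number.
- Count of previous pertussis vaccinations = 0, so the dose received is dose 1.
- Dose recommended at 4 months = dose 3.

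The share of doses mislabelled this way is u × v. Here u is the share of records without a dose number and v is the share of those given late enough, or after a missed dose, to change the label. The documents give neither.

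**2. How often a count from database opening is wrong.** Assumptions: uniform births, follow-up to age 6, no in-migration, and every dose given before opening lost. T is the number of years the database is open: 10 as an assumed value, and 18 for 1996-2013, the span of one database in Table 4. Schedule A is 2-3-4-11 months (section 5; the Dutch fourth dose is at 11 months). Schedule B is 2-4-6-18 months, where 18 months is an assumption within the second year of life.

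Children who can still receive a mislabelled dose are those between the first and last scheduled age at opening:
- A: 9 months = 0.75 birth-years. 0.75/(6+T) = 0.75/16 = 4.7%, or 0.75/24 = 3.1%.
- B: 16 months = 1.33 birth-years. 1.33/16 = 8.3%, or 1.33/24 = 5.6%.

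Mislabelled doses, out of 4T given:
- A: (1×3 + 1×2 + 7×1)/12 = 1.0. 1.0/40 = 2.5%, or 1.0/72 = 1.4%.
- B: (2×3 + 2×2 + 12×1)/12 = 1.83. 1.83/40 = 4.6%, or 1.83/72 = 2.5%.

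Share of windows labelled dose 1 that belong to a later dose (each such child contributes one):
- A: 0.75/(T+0.75) = 7.0% (T = 10), 4.0% (T = 18).
- B: 1.33/(T+1.33) = 11.8% (T = 10), 6.9% (T = 18).

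In-migration would raise these figures; any retained history would lower them.

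**3. Effect on a dose-specific estimate.** If a share m of the windows labelled with one dose belongs to another, and q is that other dose's rate (or ratio) divided by the true one, the relative bias is (1−m) + m×q. Both m and q are assumed.

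| m | q = 0.5 | q = 1 | q = 3 |
|---|---|---|---|
| 1% | 0.995 | 1.00 | 1.02 |
| 5% | 0.975 | 1.00 | 1.10 |
| 10% | 0.95 | 1.00 | 1.20 |
| 30% | 0.85 | 1.00 | 1.60 |

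**4. Whether dose number carries across schedules.** For 2+1 schedules, section 5 says "Seven countries administer a two-dose primary series at three and five months of age, followed by a booster for 12 month-olds", which puts dose 3 at 12 months. In a three-dose primary series (2-3-4 or 2-4-6) it is at 4 or 6 months. The gap is 12 − 6 = 6 to 12 − 4 = 8 months. Figure 2 places Italy and Denmark under 2+1, and the Netherlands, Spain and the UK under three primary doses. These are 2015 schedules; section 5 notes that schedules have changed over time, so the gap in the wP era may differ.

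**The case against.** Several stronger readings are tempting, and the documents do not support them.

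- *Three conflicting rules.* The number of previous vaccinations and the dose actually received are one concept. The conflict is between that concept and the per-recommendation rule.
- *Every late starter is mislabelled.* The schedule rule is stated only for records without a dose. The same bullet does mention timing in the schedule as an example of data cleaning, but only as something to be attempted.
- *A quarter to a third of children are affected.* Under the model above, children older than 2 months at opening are 5.83/(6+T), that is 36.5% or 24.3%. This measures late entry. Most of these children are past their last toddler dose and have no further window to mislabel, and earlier doses may still be on record.
- *Everything exported is per dose.* The baseline rows of Table 6 are by age.
- *wP ratios are attached to the wrong dose.* No passage says that the exported ratio is dose-specific, Figure 4 is not available in the text, and the self-controlled case series (SCCS) adjusts for age in days. The schedule gap matters for these ratios only if they are per dose.

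It is also fair to say that rates are reported by database, country and age in months, so schedule differences do not by themselves mislabel doses within a database. Schedules are a disclosed limitation, and section 7.2.9 says the results are not for direct decision-making. Deleting an undated record lowers later labels only where dose comes from sequence; a recorded number is unaffected.

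Two defences carry less weight. Precedence among dose variables could be left to a statistical analysis plan, but here the protocol itself fixes a rule that contradicts its own stratifier. The planned cross-tabulation would reveal disagreement, but it does not settle which source prevails. The Appendix 1 plots of age by dose against the schedule become circular where dose was inferred from that schedule.

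**Conclusion.** The concern holds in a limited form. For records without a dose number, section 7.2.9 assigns a dose that a late or incompletely vaccinated child did not receive, against 7.2.5, 7.2.7.1 and 7.2.8.3. A count is also too low where earlier doses are not held or an undated record is excluded.

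The size and direction of the total error are unknown. The figure of roughly 1% to 5% of doses covers only counting from database opening. It rests on uniform births, no in-migration, complete loss of earlier doses and the two schedules used; it is not an estimate for the per-recommendation rule. Age strata limit the damage but do not correct a wrong label.

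Whether dose-specific wP ratios would be carried between schedules with a 6 to 8 month gap at dose 3 is an open question that the protocol should answer, not a demonstrated error.

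**What to change.** 1. Replace the per-recommendation rule in 7.2.9 with an order of precedence: the recorded dose number; otherwise the sequence of recorded pertussis doses, if vaccination history is held from before the first scheduled dose; otherwise dose unknown, used only in rates that are not split by dose.
2. Do not silently delete an undated pertussis dose. Flag the child as dose unknown and leave that child out of the dose-specific strata and out of baseline.
3. State whether the wP ratio applied to databases without wP data is per dose. If it is, match it on primary or booster position and age, not on dose number.

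These are derivation rules to settle before the common script is run. Table 5 already collects the origin of follow-up, the count of records without a dose and the cross-tabulation of dose sources, so no new data are needed. The cost is fewer children in the dose-specific strata.

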Vaccinations: BCG, DTaP, DTwP, polio, Hib, HPV, Seasonal Influenza	Granularity of vaccine exposure data 
 
vaccine type
 
ATC code
 
brand
 
	N	Percent of total (vaccinetype) for these levels	Vaccine fingerprint
	Recorded dose vs. Derived dose vs. sequence (all possible combinations)	Cross-tabulation		Vaccine fingerprint, R
	Vaccination records without dose	N		Vaccine fingerprint, R
	Coverage in birth cohorts at age ....	Estimated Coverage (per methodology as developed in ADVANCE)	Comparison against WHO data, VENICE and local information	Vaccine fingerprint, R
	Coverage by dose	histogram of doses		Vaccine fingerprint, R
Per database and event				
Events	Name of event			
	Availability of codes	List of available codes per data domain	Frequency of each code in input files	Event fingerprint, Jerboa
	List of components	Name and description of query		Event team
	Frequency of events as detected by each component algorithm	Table of frequency of possible combinations		Algorithm comparison module of Jerboa
	Frequency of event as detected according to chosen algorithm(s)	Frequency by year		Component analysis
	Chosen algorithm and reason			Component analysis
Validity	PPV of chosen algorithm(s)	%	confidence measure	Output of the validity workflow
	Sensitivity of chosen algorithm(s)	%	confidence measure	Output of the validity workflow
	Specificity of chosen algorithm(s)	%	confidence measure	Output of the validity workflow
	Procedure to obtain the above estimates			Output of the validity workflow
External benchmarks	Validation Studies	Summaries of previously conducted validation studies in the database		Event team & database experience
	Estimates of frequency of the event in the population	Available estimates with		Event team & database

	represented by the database according to external data sources (e.g. literature)	source (and comments)		experience
--	--	-----------------------	--	------------

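### For vaccination records without a dose number, 7.2.9 derives dose from the recommended schedule, which conflicts with the received-dose definition used elsewhere and can relabel late first doses as D2 or later

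*Protocol*

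**What the plan says.** Three places in the protocol tie dose to what the child actually received.

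- Section 7.2.8.3 (Cohort Study) stratifies the incidence rates by "dose of wP/aP (actually received dose").
- Section 7.2.7.1 (Exposure Windows) says that "these periods will also be labelled by the number of previous pertussis-containing vaccinations".
- Section 7.2.5 (Population Selection) repeats the same label.

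Section 7.2.9 (Limitations) sets another rule for records that lack a dose number: "dose will be per recommendation, as determined by the database custodian based on knowledge of the local immunization schedule". The result is to be stored in an analytic variable. The same bullet gives "dose according to timing in vaccination schedule" as an example of data cleaning.

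Table 5 lists "Recorded dose vs. Derived dose vs. sequence (all possible combinations") as a cross-tabulation in the database quality sheet. Recorded, derived and sequence dose are therefore treated as separate quantities, but nothing states which of them enters the rate calculation.

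**The concern.** For a record without a dose number, the two rules can give different labels to the same vaccination. A child who starts late and whose vaccinations are all in the database has an observable order of doses, yet a schedule-based rule may label the first of them D2 or D3.

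Rates after each dose are required output: they are objective 2a in section 6 and the layout of Table 6 in section 7.3.1. Section 7.2.9 also says that risk is evaluated at dose level. First doses counted under D2, and second doses under D3, blur the contrast between doses that the benefit-risk model is to receive.

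Stratifying by age in months does not repair this. On a 2-3-4 schedule, a first dose given one month late falls at the same age as an on-time second dose. Because the custodian of each database decides the label, the error may also differ between databases.

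**Working it through.** The protocol gives no figure on this point, so there is none to reproduce.

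**Step 1: labels under a schedule-timing rule.** The primary schedules come from section 5: "either at 2-3-4 months of age (n=9) or 2-4-6 months of age (n=10"), and 3 and 5 months with a booster at 12 months. Assumption: a missing dose number is set to that of the nearest recommended age, with ties going to the earlier dose. The protocol does not spell out this algorithm. Every dose of the child is shifted by the same delay.

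| Schedule (months) | Delay of start | True doses | Label by schedule timing | Label by date order |
|---|---|---|---|---|
| 2-3-4 | 0 or 0.5 month | 1, 2, 3 | 1, 2, 3 | 1, 2, 3 |
| 2-3-4 | 1 month | 1, 2, 3 | 2, 3, 3 | 1, 2, 3 |
| 2-3-4 | 2 months | 1, 2, 3 | 3, 3, 3 | 1, 2, 3 |
| 2-4-6 | 1 month | 1, 2, 3 | 1, 2, 3 | 1, 2, 3 |
| 2-4-6 | 2 months | 1, 2, 3 | 2, 3, 3 | 1, 2, 3 |
| 3-5-12 | 1 month | 1, 2, 3 | 1, 2, 3 | 1, 2, 3 |
| 3-5-12 | 2 months | 1, 2, 3 | 2, 2, 3 | 1, 2, 3 |

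A delay of about one dose interval leaves the child with no D1 and with two doses under one later label. The date-order column is right only if all earlier doses are in the database.

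**Step 2: effect on the rate labelled D2.** Let m be the share of records without a dose number, q the share of children starting one interval late, and r1 and r2 the true rates after D1 and D2. On 2-3-4 or 2-4-6, the affected children contribute a true D1 to label D2, and their true D2 moves to label D3. The rate labelled D2 becomes

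(1 − mq) × r2 + mq × r1,

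a relative change of mq × (r1/r2 − 1).

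Inputs: r1 = 0.12% is whole-cell HHE after the first dose in the Dutch questionnaire study (section 5, Safety Studies). The protocol does not give r2, m or q. Assumed: r2 = 0.03% to 0.06%, m = 20%, q = 10%, so mq = 0.02.

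- r2 = 0.03%: 0.98 × 0.03 + 0.02 × 0.12 = 0.0318%, and 0.0318/0.03 = 1.06.
- r2 = 0.06%: 0.98 × 0.06 + 0.02 × 0.12 = 0.0612%, and 0.0612/0.06 = 1.02.

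**Step 3: range.** With the same r1 and r2, r1/r2 − 1 lies between 1 and 3.

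| m | q | mq | D2 overstatement for HHE |
|---|---|---|---|
| 5% | 2% | 0.1% | 0.1% to 0.3% |
| 20% | 10% | 2% | 2% to 6% |
| 100% | 20% | 20% | 20% to 60% |

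**Step 4: direction.** Section 5 reports that local reactions and temperature increased with later doses. Then r1 is below r2 and the change is negative: the D2 rate is too low, by at most the share mq.

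**The case against.** **The algorithm is inferred.** The derivation is left to the custodian's knowledge of the local schedule, and the timing example appears only among cleaning steps to be attempted. A custodian might refuse a history with two third doses. This stands: the labels in the table are what the wording allows, not a certain outcome. It does not remove the conflict, because the protocol still fixes a schedule-based source for a variable defined elsewhere by doses received.

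**Date order is not error-free.** Table 4 lists vaccine data as partial for DK-AUH and SE_KI. Section 7.2.9 excludes records without a vaccination date, and section 7.2.5 lets children enter at their date of valid data. A missing early record makes every later count too low. A reader might infer that the schedule rule always replaces a known dose with a wrong one. The documents do not support that, and the schedule rule has a proper use where early doses are unobserved.

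**It is partly handled.** Table 5 counts records without dose and cross-tabulates the three dose variables, Appendix 1 compares vaccination timing with the schedule, and results are reported by database. These steps would show disagreement but do not say which label is used.

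**It is a stated limitation of a proof-of-concept study.** Missing dose is listed there, but the late-start error and the conflict are not. The rates still feed the benefit-risk model.

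**Conclusion.** The conflict is real and should be resolved. It concerns only records without a dose number, and under the assumed nearest-age reading it bites for children about one interval late: one month on 2-3-4, two months on 2-4-6 or 3-5-12.

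Its size is unknown. The 2% to 6% overstatement of the D2 rate for whole-cell HHE rests on assumed m, q and r2. It may be negligible where dose is well recorded and material where it never is.

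Three stronger readings should not be drawn:

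- A reader might take the 20% to 60% end of the range as the expected error. That needs a database with no recorded dose numbers and 20% late starters, and the protocol gives neither figure.
- A reader might suppose that late starters are at different risk, for example through prematurity or illness. The protocol says nothing on why doses are late, and the conflict does not depend on it.
- A reader might take section 5 as showing that HHE and convulsions vary by dose. In the Dutch study it gives HHE for the first dose only, and very high fever and febrile convulsions for the fourth only. The increase with dose that it reports is for local reactions and temperature.

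**What to change.** Replace the missing-dose sentence in 7.2.9 with a precedence rule:

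1. Keep a recorded dose number wherever there is one.
2. If it is missing and the child's valid data start before the scheduled age of the first dose, set dose to the order of distinct recorded pertussis vaccination dates, after collapsing duplicate records.
3. Use the schedule-based number only where follow-up starts later, or where the Table 5 check shows incomplete vaccination capture in that database.
4. Flag every derived dose, with its method, in the analytic variable already planned.
5. Report dose-specific rates with and without the flagged doses.

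Sections 7.2.5, 7.2.7.1 and 7.2.8.3 should refer to this rule, so that one dose variable is used throughout.

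The cost is a short text change, a small addition to the common script including the duplicate check, and one extra set of rates. The cross-tabulation needed to judge each database is already in Table 5. The downside is that date order under-numbers doses when an early record is missing; the flag and the second set of rates make the effect visible.
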